6.1 Full Analysis Set

The full analysis set will include all randomized subjects. All subjects will be analyzed according to the treatment to which they are randomized. Full analysis set will be used for all primary analysis for primary and secondary efficacy endpoints.

6.2 Safety Analysis Set

The safety population will include all randomized subjects who received at least 1 dose of investigational product. Subjects in the analyses based on the safety analysis set will be analyzed according to the treatment group corresponding to the actual treatment received.

6.4 Pharmacokinetic/Pharmacodynamic Analyses Set(s)

The PK Concentration Analysis Set will include all subjects who received at least 1 dose of investigational product and have at least 1 PK concentration available for analysis.

7. Planned Analyses

7.1 Interim Analysis and Early Stopping Guidelines

One interim futility analysis will be performed at approximately 81 subjects completing three cycles of chemotherapy. The primary endpoint, which is the proportion of subjects with no thrombocytopenia-induced chemotherapy dose modification in the second and third cycles of the planned on-study chemotherapy regimen, will be analyzed at the interim analysis. Dose

modification assessments will be based on the central review by the independent adjudication committee. The futility boundary for the primary endpoint is p-value of 0.438, which corresponds to an OR of 1.086. The study may be stopped for futility if the non-binding futility boundary is crossed.

Due to slow enrollment, there will be no enrollment pause during the interim analysis. An independent Data Monitoring Committee (DMC) will perform the futility analysis. The DMC will make recommendation to Amgen regarding the continuation of the study. The DMC will be supported by an independent biostatistics group which is responsible for preparing reports. Details regarding the responsibilities of the DMC and the independent biostatistics group will be described in the DMC Charter.

Records of all meetings will be submitted to the TMF per the DMC Charter and in accordance with SOP-427356. Further details are provided in the DMC charter.

The Data Access Plan (DAP) will be invoked if the DMC recommends early stopping for efficacy. The DAP Team will make the decisions on further conduct of the study and will decide on any further action which may include, for example, external communication to a regulatory agency, study team, unblinding, and/or changes to study conduct. Further details are provided in the DAP.

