### Statistical Considerations

#### General Approach:

The study will have an overall alpha of 0.05 with 2-sided testing. To preserve the overall significance level, statistical testing of the primary and secondary efficacy endpoints will follow a hierarchical structure. If romiplostim demonstrates superiority to placebo for the primary endpoint, then the first secondary endpoint will be tested and so on until an endpoint is not significant or the last secondary efficacy endpoint has been tested.

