#### **10.3.1 Planned Analyses**

##### **10.3.1.1 Interim Analysis and Early Stopping Guidelines**

**One interim futility analysis will be performed at approximately 81 subjects completing three cycles of chemotherapy. The primary endpoint, which is the proportion of subjects with no thrombocytopenia-induced chemotherapy dose modification in the second and third cycles of the planned on-study chemotherapy regimen, will be analyzed at the interim analysis. Dose modification assessments will be based on the central review by the independent adjudication committee. The futility boundary for the primary endpoint is p-value of 0.438, which corresponds to an OR of 1.086. The study may be stopped for futility if the non-binding futility boundary is crossed.**

**Due to slow enrollment, there will be no enrollment pause during the interim analysis. An independent Data Monitoring Committee (DMC) will perform the futility analysis. The DMC will make recommendation to Amgen regarding the continuation of the study. The DMC will be supported by an independent biostatistics group which is responsible for preparing reports. Details regarding**

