The chosen sample size of 162 (108 romiplostim, 54 placebo) will provide 93% power to detect the treatment effect between the romiplostim group and the placebo group as defined in the

primary endpoint at a two-sided significance level of 0.05 using a Cochran-Mantel-Haenszel (CMH) test. Power calculations were performed in East version 6.4 using a 2-sided CMH test at significance level of 0.05 and stratification by tumor type and baseline platelet count ($< 50 \times 10^9/L$, $\geq 50 \times 10^9/L$).

One interim analysis will be performed at approximately 81 subjects (50% of the planned sample size) completing three cycles of chemotherapy. The non-binding futility boundary is constructed using Lan-DeMets spending function with the O'Brien-Fleming approach. Assuming an observed 35% of subjects in the control arm with no thrombocytopenia-induced chemotherapy dose modification in one cycle, the power is estimated to be 84% at the interim analysis and the probability of stopping for futility is 2%.

4. Covariates and Subgroups

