9.1 General Considerations

Continuous variables will be summarized descriptively by the n, mean, standard deviation, median, Q1 (25th percentile), Q3 (75th percentile), minimum, and maximum. The confidence interval and standard error for the mean will also be summarized for efficacy variables that are continuous. Categorical variables will be summarized descriptively by the number and percentage in each category. Missing values will be shown as a separate category. The confidence interval will also be summarized for dichotomous efficacy variables.

Time to event variables will be summarized with hazard ratios, Kaplan-Meier curves, Kaplan-Meier quartiles, the number of subjects at risk, the number of subjects censored, and the number of subjects with events.

Where confidence intervals are provided, these will be 2-sided at the 95% level, unless otherwise specified.

The primary efficacy endpoint will be compared between the romiplostim and placebo groups at the significance level of 0.05 using a 2-sided test. If statistical significance is achieved for the primary endpoint in favor of romiplostim, **the following secondary efficacy endpoints will be tested using a fixed sequence hierarchical testing procedure to control the family-wise Type I error rate below 2-sided 0.05 level. The family of hypotheses is ordered as follows:**

- the depth of platelet count nadir from the start of the first on-study chemotherapy cycle through the end of the treatment period
- the time to first platelet response, defined by platelet count $\geq 100 \times 10^9/L$, in the absence of platelet transfusions during the preceding 7 days.
- the duration-adjusted event rate of \geq grade 2 bleeding events as assessed per CTCAE version 5.0 grading scale
- overall survival
- platelet transfusion(s) during the treatment period
- achieving platelet count $\geq 100 \times 10^9/L$ at any time after study day 1 to week 4 (ie, 7 days after the planned third dose of investigational product) in the absence of platelet transfusions during the preceding 7 days

Starting with the hypothesis of platelet count nadir, if any null hypothesis in the sequence is rejected at a 2-sided significance level of 0.05, then the subsequent hypothesis will be tested; if any null hypothesis is accepted, then the subsequent hypotheses will not be tested.

Summary statistics without formal testing will be provided for other endpoints.

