9.5.1 Analyses of Primary Efficacy Endpoint(s)

The primary endpoint is the proportion of subjects with no thrombocytopenia induced dose modification. **The primary analysis will be based on the adjudication committee (AC) assessment of thrombocytopenia-induced dose modification. The proportion along with a 95% CI will be provided for each treatment group.** A 2-sided CMH test will be used to compare groups controlling for the stratification factors of tumor type and baseline platelet count. The Mantel-Haenszel estimate of common odds ratio for romiplostim vs placebo will be estimated along with a 95% CI for each treatment group and the difference in proportions between treatment groups will be provided with a 95% CI.

For primary analysis, subjects with missing observations for cycle 2 and/or cycle 3, or who discontinued any myelosuppressive agent early, are considered as not meeting the criteria of the primary endpoint. The following sensitivity analyses will be explored:

A sensitivity analysis using the investigator's assessment on thrombocytopenia -induced dose modification will be performed. The number and percentage of subjects with concordant and discordant assessments per investigator and AC will be summarized.

If more than 10% of subjects in the full analysis set have COVID-19 related IPDs with missing chemotherapy without platelet count assessment for cycle 2 or cycle 3, a sensitivity analyses may be explored by excluding those subjects with COVID-19 related IPDs.

For each specified covariate in [Section 4.1](#), sensitivity analyses will be conducted to evaluate any potential confounding: (1) a 2-sided CMH test checking conditional independence between treatment groups and primary endpoint outcomes controlling for each individual covariate, (2) a logistic regression with primary endpoint outcome as the dependent variable and explanatory variables from treatment group, the specified covariate, and interaction of treatment by covariate.

Subgroup exploratory analyses will also be performed to explore the consistency of the treatment effect between subgroups described in [Section 4.2](#). FAS will be used for the primary endpoint analysis.

9.5.2 Analyses of Secondary Efficacy Endpoint(s)**9.5.2.1 Depth of Platelet Count Nadir From the Start of the First On-study Chemotherapy Cycle Through the EOTP (1)**

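### Does the futility threshold (p 0.438, OR 1.086) need correcting because the plan never says that the p-value is one-sided?

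*SAP*

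**What the plan says.** The trial has one interim look, for futility only, at about 81 of 162 subjects. SAP 7.1 sets the threshold: "The futility boundary for the primary endpoint is p-value of 0.438, which corresponds to an OR of 1.086". It adds: "The study may be stopped for futility if the non-binding futility boundary is crossed". Protocol 10.3.1.1 carries the same rule ("The futility boundary for the primary endpoint is p-value of 0.438", again paired with 1.086).

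SAP 3.2 describes the construction: "The non-binding futility boundary is constructed using Lan-DeMets spending function", of O'Brien-Fleming type. For a control arm with a 35% per-cycle rate it says that "the probability of stopping for futility is 2" percent.

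Sidedness appears only in the efficacy testing, and there it is always two-sided. The protocol synopsis says "The study will have an overall alpha of 0.05 with 2-sided testing". SAP 9.1 says "The primary efficacy endpoint will be compared between the romiplostim and placebo groups at the significance level of 0.05 using a 2-sided test". SAP 9.5.1 says "A 2-sided CMH test will be used to compare groups controlling for the stratification factors of tumor type and baseline platelet count". Neither document mentions a one-sided p-value.

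**The concern.** A reader who takes the documents at their word would compute the two-sided stratified CMH p-value at the interim and compare it with 0.438. On that reading the two halves of the sentence disagree. At 81 subjects an odds ratio of 1.086 has a two-sided p of about 0.87 to 0.88, and a two-sided p of 0.438 belongs to an odds ratio near 1.5. Any observed odds ratio between about 1.09 and 1.5 would be futile by the p-value and not futile by the odds ratio.

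For example, 18/54 against 7/27 gives an odds ratio of 1.43. Its one-sided p is 0.25 (continue) and its two-sided p is 0.50 (futile). A two-sided p also has no direction, so a clearly harmful result could fall below 0.438 and formally not cross.

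At stake would be an avoidable recommendation to stop a trial that is already enrolling slowly.

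**Working it through.** **Inputs.** From protocol 10.1 and SAP 3.2: per-cycle rates of 30% (placebo) and 60% (romiplostim), cycle correlation 0.7, 162 subjects allocated 2:1, design odds ratio 3.6, power 93%. Interim size 81 from SAP 7.1. The 54/27 interim split is an assumption taken from the 2:1 ratio.

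**Reproducing the design.** The two-cycle rate is p² + 0.7p(1 − p).
- Romiplostim: 0.36 + 0.7 × 0.24 = 0.528.
- Placebo: 0.09 + 0.7 × 0.21 = 0.237.
- Odds ratio: (0.528/0.472) / (0.237/0.763) = 3.60 (plan: 3.6).
- Wald power for the log odds ratio at 108/54: 92.9% (plan: 93%).

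**Reproducing the boundary.** At 54/27,

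SE(log OR) = √[1/(27 × 0.237 × 0.763) + 1/(54 × 0.528 × 0.472)] = √(0.2048 + 0.0743) = 0.528.

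- One-sided 0.438: Z = 0.156, OR = exp(0.156 × 0.528) = 1.0859, which rounds to the printed 1.086.
- Two-sided 0.438: Z = 0.776, OR = exp(0.776 × 0.528) = 1.51.

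With a 35% per-cycle control rate the two-cycle placebo rate is 0.1225 + 0.7 × 0.2275 = 0.282 and the SE is 0.507. The corresponding odds ratios are 1.08 and 1.48. For a two-sided 0.438 to match 1.086, the SE would have to be 0.0825/0.776 = 0.106, which needs roughly 1,600 to 2,200 subjects.

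**Second check: the stated 2% stopping probability.** The probability of crossing when the drug works as assumed is:

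| Method | 30% control: one-sided / two-sided | 35% control: one-sided / two-sided |
|---|---|---|
| Wald, log OR | 1.2% / 4.9% | 2.8% / 9.6% |
| Exact enumeration, unstratified | 0.5% / 2.8% | 1.8% / 7.0% |
| Simulated CMH, six strata | 0.7% / 3.3% | 2.2% / 8.1–8.2% |

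The plan's 2% is given for 35% control. Only the one-sided column is near it.

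**Third check: the spending function.** If beta is 0.07 (inferred from 93% power), O'Brien-Fleming-type spending at half information allots 2 × [1 − Φ(z₀.₉₆₅/√0.5)] = 1.04%. A one-sided 0.438 uses 1.10% to 1.15%; a two-sided 0.438 would use 4.7% to 4.9%. This check is looser. The textbook boundary comes out at Z 0.118, one-sided p 0.453. Reaching 0.437 takes 92.5% power and an allowance for the non-binding look. It rules out the two-sided reading without recovering 0.438 exactly.

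**How often the two readings would conflict.** The probability that a two-sided p says futile while the odds ratio says continue is 2.0% (exact) to 2.7% (simulated) with 30% control, and 4.6% to 6.1% with 35% control. The opposite conflict has probability 0.03% to 0.18%.

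**The case for a change.** The strongest case for a change is that a pre-specified stopping rule should not rest on convention. Every test named for this endpoint is two-sided, the threshold stands in the protocol and SAP themselves, and what those sections defer to the DMC charter is chiefly responsibilities. The printed odds ratio reveals a mismatch but does not say which half governs. Even under the one-sided reading the halves can part: 19/54 against 9/27 gives an odds ratio of 1.0857 (crossed) with a one-sided p of 0.434 to 0.435 (not crossed).

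What stands is that the word is absent and would have cost nothing to include. The rest carries little weight. The sentence defines its p-value by the odds ratio beside it, so the plan excludes the two-sided reading without help from convention. Direction follows from the purpose of the look and from an odds ratio above 1. The interim test is not really open either: the primary endpoint is what is analysed, and the stratified CMH is its only planned primary comparison. The edge example turns on a gap of 0.0003 in the odds ratio, below the printed precision; with the stratified test such disagreement occurs in 0.02% to 0.08% of trials. Choosing whether the p-value or the odds ratio governs at that margin is a preference, and nothing depends on it.

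**Conclusion.** No change is needed. The threshold is unlabelled, not wrong: both printed numbers are correct, and they agree with each other and with the stated 2% only when the p-value is one-sided in favour of romiplostim.

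Harm would require someone to use a two-sided p and also disregard the odds ratio in the same sentence. Even then the conflict arises in about 2% to 3% of trials under the design alternative, or 5% to 6% with a 35% control rate. These are probabilities of crossing a boundary, not of stopping the trial. The rule is non-binding and the committee only recommends. Under protocol Appendix 3 the DMC sees treatment assignments and includes at least one external biostatistician. Type I error is unaffected, because the look offers no early claim of efficacy. Writing in the sidedness would leave the boundary, the power and the conclusions as they are.

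This rests on an interim split of 54/27, on assumed stratum shares in the simulation, and on a beta of 0.07 inferred from the stated power. Stratification moves the figures slightly but cannot bridge 1.086 and 1.5. The DMC charter was not available and may already state the sidedness.

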7.2 Primary Analysis

The primary analysis will be performed at the primary completion date. For this study, the primary completion date is defined as the date when the last subject is assessed or receives an intervention for the final collection of data for the primary endpoint. Based on the definition above, the primary completion date is either the date when the status (information on whether a given on-study chemotherapy cycle was administered as planned, administered at a modified dose, delayed, omitted or discontinued) of the third cycle of the planned on study chemotherapy regimen is assessed on the last subject or the last subject ends the last dose of investigational product plus 30 days, whichever occurs later. The data that are collected up to the primary completion date will be cleaned and locked for the primary analysis purposes. The study will be unblinded at the primary analysis.

If the study concludes prior to the primary completion date originally planned in the protocol (ie, early termination of the study), then the primary completion will be the date

when the last subject is assessed or receives an intervention for evaluation in the study (ie, last subject last visit).

Outcomes from the endpoints and assessment below will be evaluated during the primary analysis:

- no thrombocytopenia-induced modification of any myelosuppressive treatment agent in the second and third cycles of the planned on-study chemotherapy regimen.
Thrombocytopenia-induced modifications include chemotherapy dose reduction, delay, omission, or chemotherapy treatment discontinuation due to platelet counts below $100 \times 10^9/L$
- the depth of the platelet count nadir from the start of the first on-study chemotherapy cycle through the end of the treatment period
- the time to first platelet response, defined by platelet count $\geq 100 \times 10^9/L$ in the absence of platelet transfusions during the preceding 7 days
- the duration-adjusted event rate of \geq grade 2 bleeding events, as assessed by CTCAE version 5.0 grading scale

overall safety of romiplostim up to primary completion date

7.3 Final Analysis

When the last subject in the trial completes LTFU at 1 year after the last dose of investigational product, the final database will be locked for the final analysis. In the final analysis, the following secondary endpoints, assessment, and all the exploratory endpoints will be evaluated:

- overall survival
- platelet transfusion(s) during the treatment period
- achieving a platelet count $\geq 100 \times 10^9/L$ at any time after study day 1 to week 4 (ie, 7 days after the planned third dose of investigational product) and in the absence of platelet transfusions during the preceding 7 days
- overall safety of romiplostim

8. Data Screening and Acceptance

8.1 General Principles

The objective of the data screening is to assess the quantity, quality, and statistical characteristics of the data relative to the requirements of the planned analyses.

8.2 Data Handling and Electronic Transfer of Data

The Amgen Global Study Operations-Data Management (GSO-DM) department will receive and store all data to be used in the planned analyses. This study will use the database.

8.3 Handling of Missing and Incomplete Data

For primary analysis **on the thrombocytopenia-induced dose modification**, subjects with **complete missing visits (missing chemotherapy and none of the protocol specified assessments are performed) or partial visits (missing chemotherapy but some of the protocol specified assessments are performed)** without platelet count assessment for cycle 2 and/or cycle 3 are imputed as **having thrombocytopenia-induced dose modification in cycle 2 and/or cycle 3**. **Partial missing visits with platelet count assessment will be recorded following the dose modification rule in protocol section 7.4.1.2. Subjects with missing chemotherapy but having platelet count assessment within two days of the planned chemotherapy start or chemotherapy discontinuation will be determined by the adjudication committee.**

Potential **complete or partial missing or visits** missing assessments may result from below reasons:

- Death
- Early discontinuation of chemotherapy
- Consent withdrawal or lost to follow up

The rules for handling partial dates are described in [Appendix B](#)

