#### 10.2.4 Handling of Missing and Incomplete Data

For primary analysis **on the thrombocytopenia-induced dose modification**, subjects with complete missing visits (missing chemotherapy and none of the protocol specified

assessments are performed) or partial visits (missing chemotherapy but some of the protocol specified assessments are performed) without platelet count assessment for cycle 2 and/or cycle 3 are imputed as having thrombocytopenia-induced dose modification in cycle 2 and/or cycle 3. **Subjects with missing chemotherapy but having platelet count assessment within 2 days of the planned chemotherapy start or chemotherapy discontinuation will be determined by the adjudication committee.**

Potential missing visits or missing assessments may result from below reasons:

- Death
- Early discontinuation of chemotherapy
- Consent withdrawal or lost to follow up

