9.7.1 Analyses of Pharmacokinetic or Pharmacokinetic/Pharmacodynamic Endpoints

The Clinical Data Interchange Standards Consortium (CDISC) Analysis Data Model (ADaM) standard will be adopted to create the Analysis Dataset for Pharmacokinetics Concentrations (ADPC). The ADPC dataset includes the following variables: 1) subject level information (eg., subject ID, country, planned treatment, actual treatment received, population flags); 2) PK variables (eg., concentration, actual and scheduled PK sampling time); 3) Dosing variables (eg., planned and actual dose(s), start time, stop time and duration of drug infusion, time relative to first infusion start); 4) Physical measurement variables (eg., demographics, selected baseline characteristics and laboratory measurements) and 5) Miscellaneous variables (eg., study specific variables). The pharmacokinetic analysis will be carried out for PK analysis set.

10. Changes From Protocol-specified Analyses

There are no changes to the protocol-specified analyses.

11. Literature Citations / References

Collett D. Modeling Survival Data In Medical Research, Second Edition. Chapman and Hall, Boca Raton. 2003

Shapiro, S. S., and Wilk, M. B. (1965), An analysis of variance test for normality (complete samples), *Biometrika* 52, 591–611.

Van Elteren PH. "On the Combination of Independent Two-Sample Tests of Wilcoxon." *Bulletin of the International Statistical Institute* 1960;37:351–361.

12. Data Not Covered by This Plan

Further analyses of pharmacokinetic or Pharmacokinetic/Pharmacodynamic endpoints, [REDACTED]

[REDACTED]

[REDACTED]

13. Appendices

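### SAP 8.3 and 9.5.1 give up to three answers, with no order of precedence, for a cycle-2/3 visit with missed chemotherapy and a platelet count

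*SAP*

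**What the plan says.** SAP 8.3 covers subjects who miss chemotherapy in cycle 2 or 3. A visit with no platelet count is imputed as a thrombocytopenia-induced modification, that is, a failure. Two consecutive sentences then deal with visits that do have a count:

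- The first reads: "Partial missing visits with platelet count assessment will be recorded following the dose modification rule in protocol section 7.4.1.2".
- The second concerns an absent dose with a count taken close to it, and provides that anyone "having platelet count assessment within two days of the planned chemotherapy start or chemotherapy discontinuation will be determined by the adjudication committee".

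The same paragraph defines "partial visits (missing chemotherapy but some of the protocol specified assessments are performed"), so a partial visit is by definition one with missing chemotherapy.

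SAP 9.5.1 adds two statements. One is "The primary analysis will be based on the adjudication committee (AC) assessment of thrombocytopenia-induced dose modification". The other treats subjects with missing cycle-2/3 observations, or with early discontinuation of any myelosuppressive agent, as not meeting the endpoint, without reference to a platelet count or to the reason.

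Protocol 10.2.4 has the no-count rule and the committee rule ("Subjects with missing chemotherapy but having platelet count assessment within 2 days of the planned chemotherapy start or chemotherapy discontinuation" go to the committee). It has no sentence on Section 7.4.1.2. SAP Section 10 nevertheless states: "There are no changes to the protocol-specified analyses".

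**The concern.** The primary endpoint is a yes/no status per subject, so each pattern of cycle-2/3 data needs exactly one derivation. Here a partial visit with a count inside two days satisfies both sentences of SAP 8.3. The first has no time limit and no wording that confines it to the remaining cases. The overlap is the usual situation: Protocol 7.1.2 requires planned chemotherapy to start no more than 2 days after the visit laboratory tests, so a count taken on schedule normally falls inside the committee's window.

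The rules can disagree. Two programmers following the SAP could build different primary-endpoint datasets, and a choice made after unblinding would be post hoc. The primary result also gates all six secondary tests (SAP 9.1). No planned analysis compares the rules: those in SAP 9.5.1 vary the assessor, conditionally exclude COVID-19 cases, adjust for covariates, or look at subgroups.

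**Working it through.** **1. Do the sentences overlap?** A partial visit has missing chemotherapy (SAP 8.3). A partial visit with a count within two days of the planned start therefore meets the 7.4.1.2 sentence and the committee sentence together. SAP 8.3 names no order.

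**2. Can the answers differ?** The endpoint (SAP Section 5) counts modifications due to platelets below 100 x 10^9/L where the adjudicated reason is thrombocytopenia. In Protocol 7.4.1.2 the day-1 trigger for delay is below 75 for mFOLFOX6, FOLFIRINOX and mFOLFIRINOX, and below 100 for CAPEOX.

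| Subject (count within two days of planned start) | 7.4.1.2 platelet trigger | Committee, SAP Section 5 definition | SAP 9.5.1 failure sentence |
|---|---|---|---|
| mFOLFOX6, count 85, dose not given, platelets cited | No delay called for: not a thrombocytopenia-induced modification | May be a failure | Failure, if the absent dose is a missing observation |
| CAPEOX, count 85 on day 1, dose not given, platelets cited | Delay called for: failure | May be a failure | Failure, on the same condition |
| Any regimen, count 100 or above, chemotherapy stopped early for a non-platelet reason | Not a thrombocytopenia-induced modification | Not a failure | Failure |

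Row 1 is the 75-99 band, where the two sentences of SAP 8.3 can part. Row 2 shows that the gap does not arise at the CAPEOX day-1 trigger. Row 3 shows SAP 9.5.1 disagreeing with both sentences of 8.3.

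**3. The planned result.** Inputs from Protocol 10.1: per-cycle success p = 0.30 (placebo) and 0.60 (romiplostim), cycle correlation 0.7, 54 and 108 subjects. With p23 = p² + ρp(1 − p):

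- placebo: 0.09 + 0.7 × 0.21 = 0.237
- romiplostim: 0.36 + 0.7 × 0.24 = 0.528
- odds ratio: (0.528/0.472)/(0.237/0.763) = 3.60, matching the stated 3.6

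A pooled two-proportion test at two-sided 0.05 gives power 93.7% with continuity correction (95.7% without), consistent with the stated 93%. Expected successes are 0.528 × 108 = 57 and 0.237 × 54 = 12.8, taken as 13.

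**4. How much does one subject matter?** One subject is 1/108 = 0.9 percentage points of the romiplostim rate or 1/54 = 1.9 of the placebo rate. The test is the unstratified z = (p1 − p2)/√[p̄(1 − p̄)(1/108 + 1/54)]. It ignores the strata, so the planned CMH p-values will differ somewhat.

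| Romiplostim | Placebo | Two-sided p |
|---|---|---|
| 57/108 | 13/54 | 0.0005 (planned effect) |
| 57/108 | 19/54 | 0.034 |
| 57/108 | 20/54 | 0.059 |
| 43/108 | 13/54 | 0.047 (borderline) |
| 42/108 | 13/54 | 0.061 |
| 43/108 | 14/54 | 0.081 |

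For the borderline row: 0.3981 − 0.2407 = 0.1574; p̄ = 56/162 = 0.3457; standard error 0.0793; z = 1.99; p = 0.047.

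At the planned effect, seven placebo subjects must move from failure to success before significance is lost. At the borderline result, one subject in either arm is enough.

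**The case against.** The best defence is that the SAP already shows who decides. SAP 9.5.1 rests the primary analysis on the committee, SAP Section 5 counts failures by adjudicated reason, and SAP 7.1 uses central committee review at the interim analysis. The two-day sentence is the more specific rule and agrees with all three. SAP 8.3 also says that visits with a count are recorded under 7.4.1.2, whereas visits without one are imputed, so the first sentence may be only a recording instruction. Most of this stands: a reader might infer that the programmer has a free choice, and the documents do not support that, because their weight is on the committee. But SAP 8.3 does not say so. The reading also leaves counts outside two days to the 7.4.1.2 rule, and SAP 9.5.1 contradicts it in its own failure sentence.

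A reader might also infer that 7.4.1.2 ignores the reason for a missed dose, so that a cycle missed for progression at a count of 70 must be scored as a thrombocytopenia failure. The documents do not support that. Protocol 7.4.1.2 itself requires reasons other than thrombocytopenia to be captured and has an independent adjudicator verify the reason. The forced failure follows only if the section is reduced to its platelet tables.

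Nor is a count of 85 certain to split the rules. Protocol 7.4.1.2 tells investigators not to modify for thrombocytopenia above the listed levels, and Protocol 9.2.2.3 refers to the regimen guidelines as well as to 100 for discontinuation. The committee could agree with the tables. The most that can be said is that the answers could differ.

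Finally, SAP 9.5.1 plans an investigator-assessment sensitivity analysis with concordance tables. That is a useful check on who judges, but it does not test which rule applies.

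**Conclusion.** The inconsistency is real and concerns the derivation of the confirmatory primary endpoint. SAP 8.3 has two overlapping rules without precedence, SAP 9.5.1 can supply a third answer, and the added 7.4.1.2 sentence is a departure from Protocol 10.2.4 that SAP Section 10 does not declare. The clearest exposure is a non-CAPEOX subject with a count of 75-99, and any subject who stops chemotherapy early for a non-platelet reason with a count available.

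The size cannot be estimated from the documents, which give neither the frequency of missed chemotherapy with a count nor the spread of those counts. A reader might attach a number of changed subjects, but it would rest wholly on assumed shares, and on every subject at 75-99 changing status when only those the committee attributes to thrombocytopenia would. What can be said is conditional: at the planned effect a few reclassifications do not matter, while near p = 0.05 one subject can decide the result. These figures come from an unstratified test. The point does not turn on whether any dosing threshold is right.

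**What to change.** Before unblinding:

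1. In SAP 8.3, state that for missed chemotherapy with a platelet count within two days, the adjudication committee's determination, applying the endpoint definition in SAP Section 5, governs the primary analysis. This matches Protocol 10.2.4.
2. Remove the 7.4.1.2 sentence as a classifier, or keep it only as a named sensitivity analysis.
3. Say what happens to visits whose only count lies outside two days, since removing that sentence leaves them without a rule. If they also go to the committee, list this in SAP Section 10 as a change, because the two-day window is set in the protocol.
4. Limit the failure sentence in SAP 9.5.1 to visits with no platelet count, so that it agrees with 8.3 and Section 5. Deleting the 7.4.1.2 sentence alone would leave this conflict in place.

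The cost is SAP wording and possibly a few more cases for a committee that already reviews modifications in cycles 1-3. No dosing threshold changes.
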